College of Medicine
Department of Pediatrics
Division of Neonatology
Health Science Center

[name]
[name]
[name]
Office: [contact]
[contact]

Title: Research on current prototypes of the Digiclamp. Short term and long term outcomes of treating adults with achrocordons (skin tags)

NCT Number: 03259295

Date of Document: July 17, 2017

Protocol

Project Title:

"Research on current prototypes of the Digiclamp. Short term and long term outcomes of treating adults with achrocordons (Skin tags)"

Investigators:

[name]
[name]
[name], NNP
[name], NNP

Abstract:

[figure not shown]
[name] and XDG Technologies LLC have developed a proprietary, hand-held medical device (the "Digiclamp" or "device") for the treatment of both a genetic medical condition called polydactyly (i.e. extra fingers or toes) and the removal of skin tags. The current standard of care for both conditions requires a thin thread (i.e. a "suture") to be tied very tightly at the base of the extra finger/toe or the skin tag, restricting blood flow and causing the tissue to subsequently blacken and "die" (necrose) over a period of 7-14 days, then fall off. For the purpose of this study in particular we propose instead that the Digiclamp can be used to change the current standard of care for these conditions (and others) by resolving them in 10 MINUTES. This proposed project will help validate the short-term and long-term clinical efficacy of the Digiclamp specifically for treating adults who are affected by achrocordons. The use of the Digiclamp device to treat adults who suffer from this condition will demonstrate its clinical superiority over the currently accepted "standard of care" - and may lead to the clamp becoming the most common method in the U.S. The clamp procedure is the more comfortable, less costly, and more desirable option for these patients.

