depending on what method is used. Currently, there is a great need for an effective and inexpensive disposable device to remove these lesions that can be readily accessible to the primary care clinicians to use in their office. At this time, clinicians have had to rely on ligature which takes 7-14 days to resolve if successful; cryotherapy which requires expensive equipment, may be painful, and may leave an area of discoloration after the removal; cautery which is associated with pain, blistering, scarring, and also requires special equipment. Because of these associated complications, and the costs to the primary physician, they very frequently refer the patient to a sub-specialist such as a Dermatologist for this procedure. The primary caregivers have not had a reliable and inexpensive tool for removing and resolving these lesions. The Digiclamp represents a new option that when placed in the hands of these clinicians, will allow them to retain this very substantial group of patients, and to treat them without having to purchase expensive devices or to refer them to a Dermatologist. The study we are hoping to conduct will demonstrate that the Digiclamp is easy to use, quick and definitive in the removal of such lesions with less complications associated. The device is disposable, and relatively painless when used correctly, and requires minimal training. There is no need for cautery, suturing of any sort associated with the use of the Digiclamp. The procedure takes approximately 10 minutes to complete. As such, we feel that the Digiclamp is a very logical step in the management of patients with skin tags. Most importantly, in cases where the lesion requires a biopsy excision for pathologic evaluation, the Digiclamp represents a very logical option since cautery or cryotherapy may be precluded due to the effect on the tissue being removed for analysis.

VIEWS OF DIGICLAMP

Specific Aims:

The objective of the study is to treat adults with skin tags or achrocordons who wish to have these lesions removed permanently, using the Digiclamp. After removal of their lesion, these patients will be reassessed after a period of no less than 3 months and, during that visit, pictorial documentation of the lesion site will be collected to demonstrate the effectiveness of the Digiclamp in removing the lesion. The patients will then be asked to complete of a questionnaire of their satisfaction.

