Our aim is to demonstrate that the lesions removed using the Digiclamp will be resolved permanently. Also, that the site of the lesion will demonstrate minimal or no scarring, discoloration, recurrence or discomfort.

Research Plan:

We propose to enroll 25 adult patients with achrocordons to the study. These patients will have their skin tags removed by using the Digiclamp. The diagnosis the achrocordons will take place on the initial visit, and will be based on their clinical appearance of being an outgrowth of normal appearing skin attached to the underlying area by a narrow stalk. The initial visit of the study will also include photographing the lesion as well as measuring the dimensions of the skin tag (height, width).

The patients will also be asked if they have any allergy to topical anesthetic prior to removal of the skin tag. The area of the skin tag will be photographed and measured. The skin tag as well as the skin in the immediate area will then be cleaned and prepped in a sterile fashion using Chlorhexidine solution or Betadyne plus alcohol and a topical anesthetic such as Lidocaine 1% solution will be used subcutaneously or a topical cream such as Emla placed on the skin tag. The Digiclamp will then be fitted over the lesion and clamped and held in place until the lesions blanches. After 3-5 minutes, the lesion will be excised using a scalpel (#15 blade) and the clamp will be removed showing a translucent skin flap present at the base of where the skin tag had been. The area will then be covered using a small band aid, and the patient will be instructed to keep the band aid on until it naturally falls off. The patients will be asked to report any presence of post procedure bleeding, erythema, edema to the clinical coordinator after the removal.

The patients will be re-evaluated after a period of approximately 3 months for the presence of any secondary effects such as reoccurrence of the lesion, presence of scar tissue at the removal site, discoloration of the area, hyper-pigmentation, and hyper- or hypo- sensitivity.

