The inclusion criteria will be adults over the age of 18 years of age with simple achrocordons up to 1 centimeter width at the base. The exclusion criteria will include minors (less than 18 years of age), patients with lesions that are too large for adequate removal (> 1 cm at the base), whose lesions appear infected, or that are located in the genital areas or the eyelids. Also excluded are patients that have lesions that are not achrocordons and or may need their lesions evaluated by pathology, and patients with bleeding disorders.

Possible Discomforts and risks:

The potential risks in this study are minimal, but could include: (1) allergic reaction to Chlorhexidine or Betadyne solution, (2) reaction to the local anesthetic, (3) pain when compressing the base of the skin tag, (4) bleeding from the site after removal of the skin tag, (5) site infection after removal. However, during this study we will observe safeguards to mitigate potential risks. The mitigation of the risks will occur by: (1) using either Chlorhexidine or Betadyne if the patient is sensitive to either solution. (2) reaction to local anesthetic or diminution of pain will be reduced by using topical anesthetic or no anesthetic in patients whom may be sensitive to "-caine" anesthetics or have Methemoglobinemia. (3) bleeding post removal will be mitigated by excluding patients with a bleeding diathesis. (4) risk for infection at the removal site will be decreased by observing strict sterile procedure for the removal also, a sterile disposable clamp will be used for each individual procedure.

Possible Benefits:

The direct benefits to the patients will be mainly esthetic in nature. The patient will have the lesion rapidly and permanently removed when using this procedure. This procedure does not require stitch removal as would be required if excised with scalpel, without the risk of burning, or blistering as can occur with the cautery or freezing these lesions. In situations where a clinical indication to remove the skin tag exist, as is the case when these lesions become inflamed due to friction with clothing or with jewelry, the Digiclamp procedure represents an effective, less costly option readily available for use by the Primary Care personnel precluding the need for referral to a specialist. Commercially, the Digiclamp represents a new standard of care in the removal of benign skin lesions, easy to use, disposable, and inexpensive.

Conflict of Interest:

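### Early bleeding, erythema and edema are captured only if the patient volunteers a report, so no reaction and no report look the same and any short-term count would tend to be too low

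*Protocol*

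**What the plan says.** Only the protocol is at hand.

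- **Early capture (Research Plan).** The one provision is "The patients will be asked to report any presence of post procedure bleeding, erythema, edema to the clinical coordinator after the removal". It names the signs, the reporter and the recipient. It gives no day, call, visit or form, and does not ask for an answer from patients who have nothing to report.
- **Dressing (Research Plan).** In the sentence before, "the patient will be instructed to keep the band aid on until it naturally falls off". When that happens is not stated.
- **Next described assessment.** The Research Plan says "The patients will be re-evaluated after a period of approximately 3 months for the presence of any secondary effects"; the Specific Aims say "these patients will be reassessed after a period of no less than 3 months"; the Abstract gives 3 to 6 months. The effects named for the visit are late ones: recurrence, scar, discoloration, hyper-pigmentation and altered sensitivity. The list is open-ended and does not name early bleeding, erythema or edema.
- **Where early reactions bear on the study.** The title promises both short-term and long-term outcomes. The section on discomforts and risks includes "4) bleeding from the site after removal of the skin tag, (5) site infection after removal". The Background expects to show that the device is "easy to use, quick and definitive in the removal of such lesions with less complications associated".
- **Sample size (Research Plan).** "We propose to enroll 25 adult patients with achrocordons to the study", all treated with the device.

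**The concern.** A request to report the presence of a sign yields positive reports only. Silence can then mean three things: there was no sign, there was one that the patient did not notice, or there was one that the patient did not pass on. The protocol describes nothing before about 3 months that would separate them. By then bleeding, redness or swelling from the first days would have to be recalled, and asking about them is not specified.

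What is at stake is any statement about short-term reactions. If one is made from the reports received, under-reporting lowers the count. An analysis plan can say how missing answers are handled, but it cannot recover answers that were never requested. That is why the point belongs to the protocol.

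**Working it through.** **Is there a figure to reproduce?** No. The protocol gives no early reaction rate, no reporting rate and no calculation behind its sample size. The check is a reading of the text, followed by an illustration of direction.

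**Step 1: what is known about each patient.**

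| Patient's course | What the coordinator receives | Separable before the 3-month visit? |
|---|---|---|
| Sign, reported | A report | Yes |
| Sign, noticed but not reported | Nothing | No |
| Sign, not noticed (for example under the dressing) | Nothing | No |
| No sign | Nothing | No |

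The last three rows are identical in the data.

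**Step 2: direction of the error.** Inputs: n = 25 (Research Plan); p = true proportion with an early sign, assumed 5%, 10% or 20%; s = share of true reactions reported, assumed 100%, 75%, 50% or 25%. Neither p nor s is in the protocol. With no false reports,

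expected number recorded = 25 × p × s, against 25 × p true reactions.

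The recorded number falls short whenever s is below 1. For p = 10%, 2.5 reactions are expected. At s = 50%, 25 × 0.10 × 0.50 = 1.25 would be recorded.

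**Step 3: chance that no reaction is recorded.** P(0 recorded) = (1 − p × s)^25, taking patients as independent.

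| Assumed p | s = 100% | s = 75% | s = 50% | s = 25% |
|---|---|---|---|---|
| 5% | 27.7% | 38.5% | 53.1% | 73.0% |
| 10% | 7.2% | 14.2% | 27.7% | 53.1% |
| 20% | 0.4% | 1.7% | 7.2% | 27.7% |

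For example, p = 10% and s = 50% give (1 − 0.05)^25 = 0.277.

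**Step 4: what a clean record would support.** If no reports arrive and this is read as 0/25, the exact two-sided 95% upper limit is 1 − 0.025^(1/25) = 13.7%. That limit applies to reactions that are reported, that is, to p × s. It applies to the true proportion only if s = 1. At an assumed s of 50% the matching limit on p is 13.7% / 0.50 = 27.4%.

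These figures show the direction and how it depends on reporting. They do not estimate the error in this study.

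**The case against.** The case against is substantial, and much of it stands.

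- **Silence as no reaction.** A reader might infer that the protocol counts a silent patient as free of reactions. It says so nowhere. The text leaves that reading open; it does not make it.
- **The complications claim.** A reader might infer that the expectation of fewer complications rests on this reporting. The documents do not support that. The Abstract names discoloration and scarring as the complications of other methods, and the Background adds pain and blistering. None of these is bleeding, erythema or edema. Discoloration and scarring are assessed at the follow-up visit, with photographs.
- **Endpoint status.** No early rate is set as an endpoint. In the Abstract, short-term is attached to clinical efficacy, which can mean immediate removal. The title's wording is wider, and bleeding and infection are listed risks, so some relevance remains.
- **The range left open.** Presence-only reports do not by themselves exclude a high frequency. That is true of every such system by definition and is no evidence of how large the error is here.
- **Other material.** Consent and contact pages were removed, and case report forms are not at hand. An early contact might be described there, but the protocol refers to none.
- **Proportion.** For a Class 1 device with risks stated as minimal, asking each patient to report named signs to a named contact is a reasonable safety measure. As a safety measure it can stay. It is weak only as a source for a count.
- **The dressing.** That mild signs come and go unseen beneath it is possible but speculative. Signs that extend beyond it or outlast it can still be reported.

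**Conclusion.** The point holds as a minor one. The Research Plan fixes a patient-initiated, presence-only report as the sole stated capture of early bleeding, erythema and edema, with nothing further described until about 3 months. A patient without a reaction cannot be distinguished from one who did not report, and a short-term count drawn from those reports would tend to be too low.

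The amount cannot be stated from the protocol; the percentages above rest on assumed reaction and reporting rates, with only the 25 patients taken from the document. The conclusion also assumes that no unseen form already schedules an early question. It does not extend to permanent resolution, scarring, discoloration or recurrence, which are assessed at the follow-up visit.

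**What to change.** Keep the dressing instruction and the request to report signs at once. Add one sentence to the Research Plan: on a fixed early day (for example day 7, with one reminder) the clinical coordinator obtains from every treated patient, by a brief call, message or card, a yes/no answer for bleeding (including on the dressing), for erythema and for edema, and whether the band aid has come off. Day 7 is a suggestion; the protocol gives no basis for a particular day.

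If early reactions are reported, give the numbers with signs, without signs and not answering, out of all treated patients. Count no answer as missing, not as none. With 25 patients, each unanswered contact leaves 1/25 = 4 percentage points undetermined, and this should be visible in the report.

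The cost is about 25 short contacts by someone already in the plan. Some patients will not answer, and signs confined under the dressing will still go unseen, which the report should say.

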In most cases it is not necessary to treat or to remove skin tags, and usually these lesions are not bothersome. The person affected by these lesions most often would choose to remove them for cosmetic reasons if a reasonably priced, safe and effective option was available. There are instances when these growths become infected or irritated due to friction and can change in appearance, and may swell, bleed or become infected and their removal may become necessary. In these situations, as in the elective cases, there are several treatment options available to the patient. The patient may undergo suture ligature by tying a band, or a suture string at the base of the skin tag and choking off the circulation to the lesion. The patient may opt to freeze the lesions with a refrigerant such as Liquid Nitrogen or Nitrous Oxide. The lesion can also be burned off by means of an electro cautery device. Finally, the lesion can be excised using scissors or scalpel. There are no topical creams currently recommended as a medical option to remove achrocordons. The use of a topical anesthetic prior to the removal of these lesions is recommended for most of the options mentioned, however anesthesia isn't necessary. Usually, the procedure is performed by a Dermatologist in an office. Most insurance companies designate the removal of skin tags as a cosmetic procedure therefore, in most instances, their removal represents an "out of pocket" cost to the patient.

Approximately 50% of adults over the age of 45 are affected by one or more of these lesions, thereafter the risk increases with the patient's age. In most instances, a person has multiple lesions and if they desire the lesion(s) removed, the cost of removal can range anywhere from \$100 to \$300 per intervention.

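### The anesthetic safeguard, as worded, permits a '-caine' agent in the patients it is meant to protect, and the procedure step lacks its no-anesthetic option

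*Protocol*

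**What the plan says.** Three places in the Protocol bear on this.

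- **Possible Discomforts and risks, list of risks.** The risks include "reaction to the local anesthetic, (3) pain when compressing the base of the skin tag".
- **Possible Discomforts and risks, second safeguard.** One sentence answers both of these risks: "reaction to local anesthetic or diminution of pain will be reduced by using topical anesthetic or no anesthetic in patients whom may be sensitive to". It closes by naming two groups, patients sensitive to the '-caine' class and patients with methemoglobinemia.
- **Research Plan, procedure.** Before removal, "The patients will also be asked if they have any allergy to topical anesthetic prior to removal of the skin tag". After the skin is cleaned, "a topical anesthetic such as Lidocaine 1% solution will be used subcutaneously or a topical cream such as Emla placed on the skin tag".

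The inclusion and exclusion criteria at the end of the Research Plan list neither anesthetic sensitivity nor methemoglobinemia. The Background says of anesthetic use that it "is recommended for most of the options mentioned, however anesthesia isn't necessary". That remark concerns the existing ways of removing skin tags and gives no instruction for this study.

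**The concern.** A safeguard has to tell the operator which agent to avoid in which patient. This one identifies the patients clearly enough. The remedy it offers, a topical anesthetic or none, uses a term that the procedure text attaches to lidocaine 1% injected under the skin. Lidocaine is a '-caine' by name. An operator who carries the term from one section to the other would find that the rule allows the class of drug it was written to avoid.

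The step that the operator actually follows does not help. It gives the anesthetic as part of the routine and has no branch for a patient who should have none. What is at stake is an avoidable drug reaction in an elective procedure whose direct benefit the protocol describes as mainly cosmetic. Nothing in the trial's estimates or analysis depends on it.

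**Working it through.** No arithmetic applies and the protocol gives no figure to reproduce. The check sets the relevant texts side by side.

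**1. Who is protected.** The second safeguard names two groups: patients possibly sensitive to '-caine' anesthetics, and patients with methemoglobinemia. The protocol itself treats both as reasons for a different approach, so no outside source is needed to establish that they matter.

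**2. What they may receive.** The same sentence offers a topical anesthetic or no anesthetic. It names no agent, and it does not say that a topical agent must lie outside the '-caine' class.

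**3. What the protocol calls topical.** The procedure names two options.

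| Option in the Research Plan | How it is labeled | A '-caine' by name? | Stated to be outside the class? |
|---|---|---|---|
| Lidocaine 1%, subcutaneous | topical anesthetic | yes | no |
| Emla, on the skin tag | topical cream | not by name; class not stated | no |

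The label on the first row is a misnomer, because a solution given under the skin is not topical. It is nevertheless the protocol's own usage, and the only place where the term topical anesthetic is tied to a named injected drug.

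**4. Putting 2 and 3 together.** If the term keeps its procedure meaning, the safeguard permits subcutaneous lidocaine in a patient sensitive to '-caine' agents. This conclusion needs only the lidocaine wording. It does not depend on the composition of Emla, which the documents do not give.

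**5. Whether the procedure carries the exception.** The step says that an anesthetic is to be used, gives the two examples, and continues to the clamp. It has no branch without anesthetic and no reference to the safeguard. The preceding question about allergy to topical anesthetic has no stated consequence at that point; the only consequence in the document is the safeguard itself, with the wording at issue.

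**6. What the allergy question covers.** Because the procedure counts lidocaine as topical, the question as now worded does reach allergy to it, and no gap is claimed there. If lidocaine is relabeled as local or injected, the question would no longer clearly cover it. The correction has to allow for this.

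**The case against.** The strongest reply is that nobody would read the safeguard the unsafe way. The hazard is named in the same sentence, so a reading that gives these patients a '-caine' defeats the sentence's purpose. Within the risks section, the risk is a reaction to the local anesthetic and the remedy is topical or none, so topical there seems to contrast with local. The sentence also pairs two problems, reaction and pain, with two measures, topical agent and none. That suggests topical for pain in general and nothing for sensitive patients. A second reply is that the specific rule in the risks section governs the general step in the Research Plan and need not be repeated in so short a protocol.

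Much of this stands. The safe reading is plausible and probably what was meant, and an exception need not be written out twice. But the sentence does not select that reading. The contrast between local and topical, on which the reply relies, is the one that the procedure text erases by calling injected lidocaine topical. An exception that governs by implication works only if its own wording is clear.

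Four stronger inferences are tempting, and the documents do not support them:

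- **That the protocol directs lidocaine to sensitive patients.** It does not. It fails to rule this out.
- **That offering Emla to these patients is shown to be a hazard.** The documents do not state its class. It should be checked, and no more than that can be said.
- **That the lack of a methemoglobinemia question is a defect.** The protocol does not itemize history-taking. It lists no question on bleeding disorders either, and forms not shown may cover both.
- **That these patients should have been excluded, as those with bleeding disorders are.** The bleeding safeguard works by exclusion and so has to appear among the criteria ("may need their lesions evaluated by pathology, and patients with bleeding disorders"). The anesthetic safeguard works by changing or omitting the agent, so its absence from that list is expected.

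**Conclusion.** The point holds as a badly worded safety rule. The safeguard, taken in the protocol's own terms, permits the drug class it is meant to avoid, and the procedure step does not carry the no-anesthetic option that the safeguard allows. It is a cheap improvement for patient safety that should be made.

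Its size cannot be put as a rate. Of the two anesthetics named in the procedure, one is a '-caine' by name, neither is stated to lie outside that class, and there is no branch without anesthetic. How many of the 25 planned patients would have either condition cannot be derived from the documents. No endpoint, sample size or analysis is affected.

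The conclusion assumes only that an operator may take topical anesthetic to mean in one section what it means in the other. A reader might go further and infer that patients would in fact be given an unsafe agent. The text does not show that, and the probable intent was the opposite.

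**What to change.** 1. **Possible Discomforts and risks, second safeguard.** State that patients who may be sensitive to '-caine' anesthetics, or who have methemoglobinemia, receive either no anesthetic or an agent confirmed not to be a '-caine'. Check Emla against this before it is offered to them.
2. **Research Plan, anesthetic step.** Add a short cross-reference to that exception, so that giving no anesthetic is a stated option where the operator needs it.
3. **Research Plan, terminology.** Call subcutaneous lidocaine local or injected, and keep topical for agents applied to the skin.
4. **Research Plan, allergy question.** Because step 3 would narrow the existing question, reword it to ask about sensitivity to any '-caine' anesthetic by any route.

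Adding methemoglobinemia to the same question is optional. It would be sensible if no other form asks about it.

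The cost is a few wording changes and one reworded question at a visit already planned. A few patients may have the procedure without anesthetic, which the safeguard already allows. The number of patients, the visits and the analysis stay as they are.
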